#### Baseline, 6 months, and 12 months:

1. Urine pregnancy test of all female subjects
2. MRI/MRS for abdominal visceral adipose tissue, subcutaneous adipose tissue, liver fat, intramyocellular lipid content
3. Flow mediated vasodilation
4. Bionutrition: DEXA, REE, anthropometric measurements and review of a session in the lifestyle modification workbook
5. Fasting blood will be drawn for CBC, lipid profile, HgbA1c, chem 7, ALT, CD4/8, HIV viral load, aldosterone, plasma renin activity, inflammatory markers and adipokines: MCP-1, CRP, adiponectin, PAI-1, resistin, TNF $\alpha$ , TNFR2, IL-6, SHBG, total and free testosterone, LH, FSH, estradiol (females only).
6. 24 hour urine will be collected for aldosterone, potassium, sodium, cortisol and creatinine
7. Euglycemic hyperinsulinemic clamp
8. Interval medical history and physical exam including blood pressure check
9. Modifiable activity questionnaire
10. Overnight q 20 minute sampling for GH pulsatility analysis.

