#### 3 Month Visit

1. Urine pregnancy test for all female subjects
2. Physical exam, including blood pressure check, and medical history

Randomized placebo-controlled trial to investigate the effects of eplerenone in patients with HIV-associated abdominal fat accumulation

3. Euglycemic hyperinsulinemic clamp
4. Bionutrition: DEXA, anthropometric measurements, and review of a session from the lifestyle modification workbook.
5. Fasting blood: lipid profile, HgbA1c, chem. 7, CBC, potassium, creatinine, ALT, CD4/8, viral load, aldosterone, plasma renin activity, inflammatory markers and adipokines: MCP-1, CRP, adiponectin, PAI-1, resistin, TNF $\alpha$ , TNFR2, IL-6, SHBG, total and free testosterone, LH, FSH, estradiol (females only).
6. 24 hour urine will be collected for aldosterone, potassium, sodium, cortisol, and creatinine
7. Optional overnight q 20 minute sampling for growth hormone pulsatility analysis
8. Modifiable activity questionnaire

Oral Glucose Tolerance Test: A standard 75g OGTT will be performed on the morning of the screen visit following a 12 hour fast, with interval measurements of insulin and glucose at 0 and 120 min.

Euglycemic-Hyperinsulinemic Clamp: After 12-h overnight fast, patients will receive a primed infusion of regular insulin mixed with albumin, 80 mU/m^2, for 2 hours, with a variable rate of dextrose administered to maintain blood glucose at 5.0 mmol/L (90 mg/dL). Blood samples will be collected for glucose at time 0 and every 5 min during the 2-hour clamp, and samples for insulin will be collected every 20 min from 0-120 minutes. Insulin sensitivity will be calculated.

Optional GH Pulsatility Analysis: Starting at 2000 until 0740 the next morning, fasting blood will be sampled every 20 minutes. Approximately 1.5cc of blood will be drawn at each time point for a total of 54cc. Mean overnight GH concentration, basal concentration, pulse frequency, pulse amplitude and overall pattern regularity will be determined using the deconvolution analysis and cluster computerized pulsatility program.

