DEXA (Hologic) will be used to determine whole body and regional fat will be assessed. The technique has a precision error (1 SD) of 3% for whole body fat and 1.5% for lean mass. It estimates body composition from the attenuation of X-rays pulsed in synchrony between 100 and 140 kV with the line frequency for each pixel of the scanned image. (As an external standard for analysis of body composition, a step phantom, with six fields of acrylic and aluminum of varying thickness and known absorptive properties, was scanned periodically for calibration.) The DEXA scan will be used to determine total body fat as well as regional body fat measurements.

Anthropometric Measurements

Subjects' height and weight will be obtained and plotted on standard weight charts to determine percent of ideal body weight. Body mass index will be calculated. Anthropometric measurements of waist to hip ratio, leg circumference, arm circumference and neck circumference will be performed using a standardized technique. Waist-to-hip ratio will be determined from the circumferential measurements of the iliac waist and the hips at the level of the iliac crest taken with the patient in an upright standing position.

Bionutritional Analysis: Protein, carbohydrate, fat, micronutrient, dietary supplements and alcohol intake will be determined from 4-day food records (3 weekdays and 1 weekend day) (Nutrition Data systems).

High Sodium Diet: A high sodium diet will be followed for 6 days prior to the Baseline, 3, 6 and 12 month visits and consists of the subject's normal, ad lib diet supplemented with high sodium meals and/or chicken broth, and snacks to equal approximately 200 mEq of sodium. The 7th day (last day) of the high sodium diet will be completed on the first day of the Baseline, 3, 6 and 12 month visit.

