## VI. Biostatistical Analysis

The primary endpoint will be change in insulin stimulated glucose uptake as measured by euglycemic clamp. Secondary endpoints include change in levels of adipokines and endothelial function. In addition, we will assess eplerenone's effects on hepatic fat and IMCL. VAT and SAT will be measured simultaneously and controlled for in the analyses of hepatic fat and IMCL. Randomization will be stratified by gender, age (< or > 45), and BP (SBP >140 or DBP>90, or normotensive). Wilk-Shapiro test will be used to assess for normality of distribution of all variables, and variables that are not normally distributed will be log-transformed. Baseline variables will be compared between treatment groups by t-test for continuous variables and Wilcoxon Rank Sum test for variables that are not normally distributed. Any baseline variable that is statistically different between treatment groups will be adjusted for in subsequent analysis. We will analyze the entire set of repeated measurements (baseline, 3 and 6 mos) by using the longitudinal mixed effects model, using all available data, including interim data from those who do not complete the study, to determine differences in longitudinal mean changes between eplerenone and placebo over 6 mos of treatment (i.e., test for time x group interaction). The analyses will be intention to treat, using all interim data for subjects who do not complete the study. We will control for gender, race, anti-hypertensive and lipid lowering medication use, urine free cortisol, dietary intake (caloric, macronutrient, alcohol, supplements, salt intake), activity, ARV use and smoking. We will analyze the dietary data in terms of overall caloric intake and macronutrient composition, to determine whether there are any differences in diet by study treatment, or whether change in dietary intake patterns, including vitamins, affects the treatment results. Similar analyses will be performed for activity using the Modifiable Activity Questionnaire. In a sensitivity analysis if the dropout rate is higher than expected or differs between groups, we will

Randomized placebo-controlled trial to investigate the effects of eplerenone in patients with HIV-associated abdominal fat accumulation

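### The primary model is promised on all available data under intention to treat, but it adjusts for urine cortisol, diet and activity with no rule for missing covariates, so a standard fit may drop clamp values already obtained.

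*Combined protocol and SAP*

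**What the plan says.** All of the analysis text is in section VI (Biostatistical Analysis) of the combined protocol and SAP.

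- **Model:** "We will analyze the entire set of repeated measurements (baseline, 3 and 6 mos) by using the longitudinal mixed effects model", with the treatment effect tested as a time-by-group interaction.
- **Data rule:** the model is to be fitted "using all available data, including interim data from those who do not complete the study", and "The analyses will be intention to treat, using all interim data for subjects who do not complete the study".
- **Adjustment:** "We will control for gender, race, anti-hypertensive and lipid lowering medication use, urine free cortisol, dietary intake". The sentence continues with the dietary components and further items: "dietary intake (caloric, macronutrient, alcohol, supplements, salt intake), activity, ARV use and smoking".

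Three of these covariates come from collections separate from the clamp:

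- **Urine free cortisol** comes from the 24-hour urine. The list for baseline, 6 and 12 months has "24 hour urine will be collected for aldosterone, potassium, sodium, cortisol and creatinine", and the 3-month list has "24 hour urine will be collected for aldosterone, potassium, sodium, cortisol, and creatinine".
- **Diet** comes from the food record. The Bionutritional Analysis paragraph of section V says "dietary supplements and alcohol intake will be determined from 4-day food records (3 weekdays and 1 weekend day". The visit lists name that record only at the screen visit, where it is handed out. The bionutrition items at baseline, 3 and 6 months do not include it.
- **Activity** comes from the Modifiable Activity Questionnaire, listed at baseline, 3, 6 and 12 months.

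The only missing-data method is a last-observation-carried-forward sensitivity analysis, used if dropout exceeds expectation or differs between groups. The plan does not say what happens when a covariate is missing, or whether covariates enter as baseline or visit-level values. It writes down no unadjusted primary model.

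**The concern.** A likelihood-based mixed model copes with a missing outcome because the subject's other visits still contribute. It does not cope in the same way with a missing covariate. The model is conditional on the covariates, so a row lacking one cannot be used unless the value is filled in or modelled. The property that justifies the all-available-data claim therefore covers missing clamps, not missing urines, food records or questionnaires.

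A subject can complete a supervised clamp and still fail to return one of the other three items. The carried-forward analysis does not help, because that subject has not dropped out. As written, the plan leaves the analyst to choose after the data are in: drop such rows, impute, or drop the covariate. Dropping rows would discard measured primary outcomes and leave an analysed set smaller than the randomised set.

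This is separate from the question of adjusting for variables measured after randomisation. It remains if every covariate is a baseline value.

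**Working it through.** **Step 1. Reproduce the plan's power.** The inputs are in the Sample Size Calculation of section VI: 25 evaluable patients per group, a difference of 0.8 SD, P = 0.05 and an independent-samples t-test. Sidedness is not stated; two-sided is assumed. The noncentrality is 0.8 × √(25/2) = 2.83 on 48 degrees of freedom, with critical value 2.01. Power is 79.1% by the noncentral t, or 80.7% by the normal approximation. The stated 80% is reproduced. A one-sided test would give 87.4%, so the figure is two-sided.

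**Step 2. What a standard fit would drop.**

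- Visit-level covariates: a missing item at 3 months removes the 3-month clamp and leaves that subject's other visits in.
- Baseline covariates: a missing item at baseline removes all of that subject's clamps.

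The plan does not say which reading applies. The illustration below is for the baseline reading only, because only there does a lost covariate equal a lost subject.

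**Step 3. Size, over an assumed range.** The documents give no missingness rate. Let *q* be the fraction of subjects missing each of the three sources, taken as 3%, 5% or 10%, and treat 25 per group as the count before covariate losses. Two patterns are shown:

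- missing independently: kept fraction (1 − *q*)³
- always missing together: kept fraction 1 − *q*

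Power is the two-sided noncentral t at 0.8 SD with the resulting number per group.

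| *q* per source | Independent: kept | n per group | Power | Together: kept | n per group | Power |
|---|---|---|---|---|---|---|
| 0% | 1.000 | 25 | 79.1% | 1.00 | 25 | 79.1% |
| 3% | 0.97³ = 0.913 | 22.8 | 75.2% | 0.97 | 24.3 | 77.9% |
| 5% | 0.95³ = 0.857 | 21.4 | 72.5% | 0.95 | 23.8 | 77.0% |
| 10% | 0.90³ = 0.729 | 18.2 | 65.1% | 0.90 | 22.5 | 74.6% |

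The urine and the questionnaire belong to the same visits, so some overlap in missingness is plausible, and the truth may lie between the two patterns. The table uses the plan's simple t-test and ignores any precision gained from repeated measures or from the covariates.

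**The case against.** The strongest reply is that the plan never says rows will be deleted. Deletion is how a standard fit behaves, and the stated intent points the other way. A statistician holding to that intent would impute or leave the covariate out. This stands in part: the plan has not prescribed a complete-case analysis. But it has not prescribed anything else, and the two statements cannot both be honoured without a rule.

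Second, the full covariate list may not belong to the primary analysis. That analysis is named as the 6-month comparison, it is powered by an unadjusted t-test, and diet and activity are then described as questions to be explored. This reading is possible. The adjustment sentence, however, carries no condition and follows directly on the mixed model.

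Third, a reader might infer that power will fall below 80%. The documents do not establish that. 'Evaluable' is undefined and no number to be randomised is given. If 25 already means patients with complete covariates, subtracting losses from it counts them twice. The missingness rates and patterns are also assumptions.

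Fourth, a reader might infer from the visit lists that no diet value will exist at 3 or 6 months, so that every later clamp would be lost. That goes too far. The Bionutritional Analysis paragraph sets no such limit, and section VI plans to analyse change in diet, so later records are evidently intended. Nor do the documents show that subjects with incomplete collections differ from the rest. That is a possibility only.

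**Conclusion.** The point holds as a conflict left open in the plan: all-available-data and intention-to-treat wording beside a model whose covariates come from three separate collections, with no missing-covariate rule and no unadjusted primary model. A standard fit of that model may drop clamp values already measured.

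Its size cannot be fixed from the documents. On the baseline-covariate reading, with 25 per group before losses, 3% to 10% missing per source costs between about 1 point of power (79.1% to 77.9%, 3% missing together) and 14 points (79.1% to 65.1%, 10% missing independently). The visit-level reading would lose single visits rather than subjects, and these figures do not apply to it. The correction is worth making because it is cheap and removes a choice that would otherwise be made after the data are seen.

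**What to change.** In section VI:

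1. State that the primary model is fitted to every randomised subject with a clamp value. It contains treatment, time, their interaction, and baseline covariates only: the stratification factors (gender, age, blood pressure) and simple history items such as race, medication use, antiretroviral use and smoking.
2. State that a missing baseline covariate is filled with the pooled mean, or with a 'missing' category for categorical items, without regard to arm. This rule is for baseline values only; it is not justified for covariates measured after randomisation.
3. Move adjustment for urine cortisol, diet and activity to a secondary model that reports the number of clamp values used, by arm and visit. Say there whether those covariates enter at baseline or by visit, and reconcile the food-record schedule in section V with the planned diet analyses.

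The cost is SAP wording and minor programming, with no new data collection for the primary model. The downside is a possible small loss of precision in the primary model, from leaving out the urine, diet and activity covariates and from single fill-in of baseline values.

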### **Sample Size Calculation**

Assuming 25 evaluable patients in each group, the study will have 80% power to detect a between groups difference of 0.8 SD in the percent change over 6 mos, at P=0.05 by an independent samples t-test. Thus the power of the longitudinal mixed models approach will be greater than the first-and last pair analysis. Based on data from our group, mean $\pm$ SD of insulin stimulated glucose uptake in this population using our clamp protocol is  $7.4\pm1.7$ mg/kg/min. The current study will be powered to detect a change in glucose uptake of 1.4mg/kg/min, or approximately 20% change, which would be physiologically relevant.

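### The 80% power figure reproduces, but the claim that the mixed model has greater power does not follow from it. A month-6 contrast that is always adjusted for baseline and the stratification factors costs almost nothing.

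*Combined protocol and SAP*

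**What the plan says.** Section VI, Biostatistical Analysis, defines the endpoint: "The primary endpoint will be change in insulin stimulated glucose uptake as measured by euglycemic clamp". The analysis is a longitudinal mixed model of baseline, month 3 and month 6, "using all available data, including interim data from those who do not complete the study", and its purpose is "to determine differences in longitudinal mean changes between eplerenone and placebo over 6 mos of treatment (i.e., test for time x group interaction". Later in the section the comparison of the arms after 6 months is named as primary, but it is not tied to a contrast in that model.

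The covariate list begins: "We will control for gender, race, anti-hypertensive and lipid lowering medication use, urine free cortisol, dietary intake". It goes on to activity, antiretroviral use and smoking. It contains gender, but not the age and blood-pressure factors by which randomisation is stratified. Other baseline variables enter by a test: "Any baseline variable that is statistically different between treatment groups will be adjusted for in subsequent analysis". On scale, "variables that are not normally distributed will be log-transformed".

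The Sample Size Calculation gives 80% power at P=0.05 for a difference of 0.8 SD in percent change, by an independent-samples t-test with 25 evaluable patients per group. It adds: "Thus the power of the longitudinal mixed models approach will be greater than the first-and last pair analysis". It then gives a mean and SD of glucose uptake of 7.4 and 1.7 mg/kg/min, and says that the trial is powered for 1.4 mg/kg/min, about 20%.

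**The concern.** The sentence about greater power presents as a consequence something that a t-test calculation cannot deliver. Whether a mixed model beats a first-to-last comparison depends on how time is coded, the covariance structure, the treatment of baseline and the timing of the effect. None of these is given.

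The target in mg/kg/min is also not linked to the powered quantity. The endpoint is change, the powered quantity is percent change, and the only SD given is that of the level. A reader cannot tell what power the trial has for the effect that it calls physiologically relevant.

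The baseline clamp value usually predicts the follow-up value, yet the plan adjusts for it only if the arms happen to differ significantly. Two of the three stratification factors are not in the fixed list. Urine cortisol is measured again on treatment ("24 hour urine will be collected for aldosterone, potassium, sodium, cortisol, and creatinine"), and the plan does not say whether baseline or on-treatment values enter the model. If on-treatment values entered, the adjusted difference need not be the total treatment effect.

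**Working it through.** **Inputs from the Sample Size Calculation:** n = 25 per arm, alpha 0.05 (two-sided assumed, as the plan does not say), effect 0.8 SD, mean 7.4, SD of level 1.7, target 1.4 mg/kg/min. **Assumed, because the plan does not give them:** the baseline to month-6 correlation rho, and the month-6 SD (1.7, or 2.0 as a less favourable case).

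**1. The plan's own figure.** Non-centrality is 0.8 × √(25/2) = 2.83 on 48 df. Power is 79.1% (80.7% by the normal approximation). The stated 80% reproduces.

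**2. The 1.4 mg/kg/min target.** 0.8 × 1.7 = 1.36, close to 1.4, and 1.4/7.4 = 18.9%. So the target appears to use the SD of the level; this is an inference, as no derivation is shown. With equal SDs, SD of change = 1.7 × √(2(1 − rho)), which equals 1.7 only at rho = 0.5. Exact 80% power needs a standardised difference of 0.809, so the largest SD of change is 1.4/0.809 = 1.73 (rho about 0.48).

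**3. The mixed-model claim, with 0.8 SD of change at month 6 and complete data.**
- *Linear time, 1 df, baseline means unconstrained.* The generalised least squares weights on months 0, 3 and 6 are (−1, 0, 1) under compound symmetry and AR(1). Month 3 adds nothing and power stays at 79.1%.
- *Categorical time, 2 df (non-central F).* 69–70% with linear build-up. With the full effect by month 3, 82–83% under compound symmetry and 91–92% under AR(1) with rho 0.7 between adjacent visits.
- *Baseline adjusted.* The month-6 contrast has 89% under compound symmetry 0.5, 89% under AR(1) 0.7, and 91% under correlations of 0.5 (months 0–3), 0.4 (0–6) and 0.7 (3–6). Constraining baseline means to be equal gives similar figures with linear build-up.
- *Non-completers.* Adding 3 or 6 patients per arm seen only at months 0 and 3 raises the linear test to 80–81% or 82–83%.

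**4. Gain from baseline adjustment, for 1.4 mg/kg/min with 25 per arm.** The change score has SD √(s0² + s6² − 2·rho·s0·s6). The adjusted contrast has residual SD s6 × √(1 − rho²), on 47 df, with variance factor 47/46 for estimating the slope.

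| Month-6 SD | rho | SD of change | Power, change score | Residual SD | Power, adjusted |
|---|---|---|---|---|---|
| 1.7 | 0.3 | 2.01 | 67% | 1.62 | 84% |
| 1.7 | 0.5 | 1.70 | 81% | 1.47 | 90% |
| 1.7 | 0.7 | 1.32 | 96% | 1.21 | 98% |
| 1.7 | 0.8 | 1.08 | 99.5% | 1.02 | 99.7% |
| 2.0 | 0.3 | 2.20 | 60% | 1.91 | 71% |
| 2.0 | 0.5 | 1.87 | 74% | 1.73 | 79% |
| 2.0 | 0.7 | 1.46 | 91.4% | 1.43 | 91.9% |

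**5. Cost of further covariates (SD 1.7).** With k covariates including baseline, df = 48 − k and the variance factor is 47/(47 − k). Three further non-prognostic terms (k = 4) give 82% and 88% at rho 0.3 and 0.5. Simulation with three balanced binary factors gives 85% and 90%, so balanced stratification factors cost little. Eleven further non-prognostic terms give 73% and 81%. That is a worst case, since prognostic covariates would recover some of the loss.

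**The case against.** A reader might infer that the trial is underpowered. The documents do not support that. The 80% is right, and 1.4 mg/kg/min agrees with it if the SD of change is about 1.7. That assumption is undocumented, not shown to be wrong. Nor does the sample size rest on the mixed-model sentence, since the trial is sized on the t-test.

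A reader might also infer that the sentence is false. It is true in several standard forms. Baseline is already a repeated measurement in the planned model, and constraining its means to be equal would bring a clear gain. Partial data from non-completers help a little. What stands is that the claim cannot be derived from what is written.

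It is tempting to say that the covariates and scale are left open until the data are seen. They are not. The covariate list is named in advance, and so is the rule for log transformation. Only the baseline variables chosen by a significance test depend on the data, and that too follows a stated rule. Section VI also describes separate analyses of dietary change and activity. This weakens, without excluding, the reading that on-treatment values enter the main model. Still unspecified are the time coding, the covariance structure, the link between the interaction test and the month-6 comparison, and which covariate values are used.

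Finally, the gain is not general. It is measured against a change-score t-test and almost disappears at high correlation.

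**Conclusion.** The point holds as a low-cost improvement and a correction of one inference; it is not an error in the sample size. The greater-power sentence is unsupported as written: depending on the specification, power at 0.8 SD of change runs from about 69% to about 92% in the complete-data cases shown. Unconditional baseline adjustment is worth about 17 points at rho 0.3 and 9 at rho 0.5 if the SD is 1.7 at both visits, but only about 2 at rho 0.7 and almost none at 0.8. If the month-6 SD is 2.0, the gains are about 11 and 5 points at rho 0.3 and 0.5, with no material gain at 0.7 or above. In that case adjusted power remains below 80% at rho 0.5, so 80% should not be claimed for every correlation. Every rho and the SD of 2.0 are assumptions. The plan should be changed on this point, but nothing here calls for more patients.

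**What to change.** - Make the primary test the month-6 eplerenone–placebo difference, the comparison that Section VI already names. Take it from a mixed model with categorical visit, treatment-by-visit and a named covariance structure.
- Always adjust for baseline glucose uptake (or constrain baseline means to be equal) and for the gender, age and blood-pressure strata.
- Drop the significance rule for baseline variables from the primary model. Use only baseline values of any other covariate kept there, and move the rest of the list to sensitivity analyses.
- Delete the greater-power sentence, or make it conditional on the baseline adjustment.
- State the SD of change or the correlation behind 1.4 mg/kg/min, from the group's own repeat clamp data if they exist. If not, give a range with its assumptions, as in the table above.

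The cost is SAP wording and a few degrees of freedom. No patient, visit or clamp is added.

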use a LOCF approach carrying forward the last available data to use in the analysis, to determine if the dropouts affected the results. All patients cross-over to open label eplerenone from mos 6 to 12. The primary analysis will be the comparison of placebo and eplerenone after 6 months and the purpose of the open label design after 6 mos is to encourage recruitment and retention. Safety data will be collected at all time points and continued treatment over 12 mos will allow us to determine safety and tolerability over one year and whether changes in critical endpoints continue to improve with one year of dosing.

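### The claim of power for a 1.4 mg/kg/min change is unsupported because it appears to apply a 0.8 SD effect in percent change to the SD of the glucose uptake level

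*Combined protocol and SAP*

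**What the plan says.** The Sample Size Calculation makes three statements about the primary endpoint.

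- With 25 evaluable patients per group and an independent-samples t-test at 0.05, "the study will have 80% power to detect a between groups difference of 0.8 SD in the percent change over 6 mos".
- The group's own data give 7.4 ± 1.7 mg/kg/min, described as the mean and "SD of insulin stimulated glucose uptake in this population using our clamp protocol".
- "The current study will be powered to detect a change in glucose uptake of 1.4mg/kg/min, or approximately 20% change", which the plan regards as physiologically relevant.

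It also says that "the power of the longitudinal mixed models approach will be greater than the first-and last pair analysis", without giving a size for the gain.

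VI. Biostatistical Analysis defines the endpoint without a scale: "The primary endpoint will be change in insulin stimulated glucose uptake as measured by euglycemic clamp". It then plans a mixed model on the baseline, 3-month and 6-month values, tested through the time by group interaction, "to determine differences in longitudinal mean changes between eplerenone and placebo over 6 mos of treatment". Later in the same section, "The primary analysis will be the comparison of placebo and eplerenone after 6 months".

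**The concern.** The power statement is in SDs of percent change, while the only SD reported is that of the level. Moving from 0.8 SD to an effect in mg/kg/min needs the SD of the change (or of the percent change), or the correlation r between baseline and 6 months. None of these appears anywhere in the plan.

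The 1.4 figure carries the clinical argument for the sample size. After a null result it would be cited to say that the trial had 80% power for an effect of that size. If r were 0.3, the chance of missing a true 1.4 would be 33%, not 20%. The mismatch also leaves it unclear whether the primary comparison is of absolute change, percent change or 6-month values.

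**Working it through.** **Inputs from the plan:** 25 evaluable per arm, alpha 0.05 (taken as two-sided, since a one-sided test would give 87%), effect 0.8 SD, level mean 7.4 and SD 1.7 mg/kg/min, target 1.4 mg/kg/min.

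**Assumed:** r, which the plan does not give, and an SD of 1.7 at both visits.

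**1. The plan's own figure.** For a standardised difference d, the noncentrality is d / sqrt(2/25). With d = 0.8 this is 0.8 / 0.2828 = 2.83. Power is 79.1% from the exact t-test on 48 df and 80.7% from the normal approximation. The stated 80% reproduces. Exactly 80% needs d = 0.8087.

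**2. Where 1.4 seems to come from.** 0.8 x 1.7 = 1.36, close to 1.4, and 1.4 / 7.4 = 18.9%, close to the stated 20%. This is an inference from the arithmetic.

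**3. What the claim requires for a comparison of changes.**

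- Absolute scale: the SD of change must be at most 1.4 / 0.8087 = 1.73 mg/kg/min. Since SD of change = 1.7 x sqrt(2(1 − r)), this means r of at least 1 − (1.73/1.7)²/2 = 0.48.
- Percent scale: the SD of percent change must be at most 18.92 / 0.8087 = 23.4 points for an 18.9% effect, or 20 / 0.8087 = 24.7 points for 20%.

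**4. Power for 1.4 on each analysis.** The change score uses 48 df. The single 6-month comparison adjusted for baseline has residual SD 1.7 x sqrt(1 − r²) and 47 df.

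| Assumed r | SD of change | Power, change score | Detectable at 80%, change score | Residual SD, adjusted | Power, adjusted |
|---|---|---|---|---|---|
| 0 | 2.40 | 52% | 1.94 | 1.70 | 81% |
| 0.3 | 2.01 | 67% | 1.63 | 1.62 | 85% |
| 0.5 | 1.70 | 81% | 1.37 | 1.47 | 91% |
| 0.7 | 1.32 | 96% | 1.06 | 1.21 | 98% |

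The level SD equals the SD of absolute change only at r = 0.5.

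**5. Which column the planned analysis resembles.** A time by group test that treats baseline as one of the repeated outcomes behaves, for complete data, like a difference in mean changes. The change-score column is therefore the nearer guide to the model as written.

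**6. Sensitivity of the adjusted figures.** If the 6-month SD were 2.0 (assumed) rather than 1.7, adjusted power for 1.4 would be 68% at r = 0 and 72% at r = 0.3.

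**The case against.** The strongest reply is that nothing stated is shown to be wrong. The 80% reproduces, 1.36 rounds to 1.4, and 18.9% is fairly called about 20%. This stands: the fault is an unstated assumption, not an arithmetic error. The 0.8 SD sentence also justifies 25 per arm by itself, but only in SD units.

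A reader might infer that the trial is underpowered. The documents do not support that: the 67% comes from choosing r = 0.3, and the same calculation gives 96% at r = 0.7.

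It can also be said that the level SD is the right one, because the plan elsewhere describes the primary analysis as a comparison after 6 months. On that reading 1.7 gives 81% power for 1.4. The reading is possible but not settled: the endpoint is defined as change, the planned test is the interaction, and the power sentence refers to percent change.

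The expected gain from the mixed model does not fill the gap. Its size is not given, and it does not say what 0.8 SD is in mg/kg/min.

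Finally, a reader might take "variables that are not normally distributed will be log-transformed" as evidence that the primary endpoint could be analysed on a third scale. That sentence is general and conditional on non-normality, so it is weak evidence about this endpoint. The wording on change and percent change is loose, but it is not a contradiction.

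**Conclusion.** The concern holds as a gap in support. The 80% power for 0.8 SD is correct. The claim of power for 1.4 mg/kg/min does not follow from the figures given, because for a change-score or time by group comparison it needs an SD of change no larger than about 1.73 mg/kg/min (r about 0.48 or more, equal variances assumed), and the plan states neither. Whether power for 1.4 is above or below 80% cannot be determined from the documents. All results by r rest on assumed correlations and an SD of 1.7 at both visits.

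**What to change.** Make the primary analysis the between-group difference at 6 months in glucose uptake, in mg/kg/min, adjusted for baseline glucose uptake. This can stay within the planned mixed model, with the 3- and 6-month values as outcomes and baseline as a covariate, so interim data are kept. Align VI. Biostatistical Analysis and the Sample Size Calculation with this before unblinding.

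Then restate the power on that scale, with the assumption named. With SD 1.7 at both visits, 1.7 is an upper bound for the residual SD, and a single adjusted 6-month comparison has at least about 81% power for 1.4 at any r from 0 up. The text should say that the figure falls if the 6-month SD exceeds 1.7. The SD of change or r from the group's own repeated clamp data, if available, would firm it up.

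If the change-score analysis is kept, drop the 1.4 mg/kg/min claim or restate it as a range over r, as tabulated above.

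The cost is a short amendment to the analysis wording and a stated figure that depends on a named assumption. The baseline clamp is already collected, and enrolment does not change.
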